- C) Blood sampling for metabolomics analysis (Aim 3): Baseline and serial study blood for processing as below will be drawn between 0800 and 1000 h. at the baseline day and study days 3, 7, 14, 21 and 28. A total of 28 mL of blood will be drawn at baseline and days 7, 14, 21 and 28 of study. A total of approximately 150 mL of blood will be obtained for analysis during the first 28 days after entry.
- D) Assessment and monitoring of blood glucose concentrations: Three blood glucose data points (the initial AM blood glucose sent to the hospital laboratory, and one representative laboratory or fingerstick blood glucose level obtained at a time point between 1400-1660 h and again between 2200-2400 h) \pm 1 hour window.
- E) Assessment and monitoring of nosocomial infections: New hospital infections will be diagnosed based on standardized CDC criteria exactly as currently performed in [name] multicenter NIH U01 study (updated by CDC in 2009). All infections will be adjudicated by review of pertinent data in a blinded fashion by Infectious Disease Co-I [name].
- F) Stool sampling for microbiome analysis (Aim 3): Stool samples, when available, will be collected by the primary nurse at baseline and study days 3, 7, and 14, within 24 hours of the specific study day. The sample will be placed in a vial and frozen for later analysis by colleagues at the University of Chicago. The date, time, and consistency of stool will be collected for each sample.
- G) Handgrip strength test for overall strength assessment (Aim 3): If patients are deemed alert and able by study team, a Jamar Hydraulic Hand Dynamometer (Sammons Preston Rolyan, Chicago, IL) will be used to measure handgrip strength on the day subjects leave the ICU, then 3 and 7 days after ICU discharge. If the subject is consented before surgery and subsequent ICU admission, a handgrip measurement will be taken during pre-op. At each time point, the subject will be asked to squeeze the handheld dynamometer as hard as they can for 3 seconds, and they will be asked to repeat this 3 times, with a 1-minute rest between measurements.

Serial data entry via case report forms (CRFs): The investigators will monitor all study subjects daily during the ICU stay and after discharge to the general ward and enter data into

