gut microbiota in all fecal samples will be identified using established next generation DNA sequencing of 16S rRNA libraries, performed by our collaborator [name] of the University of Chicago (6, 18, 66). Briefly, 50 mg of frozen fecal sample will be homogenized in extraction buffer and 0.1-mm-diameter zirconia/silica beads are added prior to lysing of microbial cells on a Mini-Beadbeater-8 cell disrupter. After overnight incubation at 55°C, extraction with phenol: chloroform: isoamyl alcohol, and precipitation with ethanol will be performed. Isolated DNA is dissolved in Tris-EDTA buffer and stored at -80°C. The 16S rRNA gene sequences are amplified from DNA samples using barcode-labeled primers for the V3–V4 region of the 16S rRNA encoding gene (*Escherichia coli* positions 338–806), as outlined^{65–67}. The Shannon diversity index and distinctive peak numbers (richness) of the OTUs in the microbiome libraries between baseline (day 0) and serial fecal samples (days 3, 7, and 14) will be compared as previously outlined^{65, 67, 68}. These representative sequences are aligned using PyNAST and taxonomy assigned to them using the RDP Classifier. The PyNAST-aligned sequences will also be used to build a phylogenetic tree with FastTree and unweighted UniFrac distances then computed between all samples for additional ecological analyses, including principal coordinates analysis (PCA)^{65–67}.

Adverse Event (AE) Reporting:

The subjects enrolled in this trial are initially critically ill subjects deemed to require both PN and prolonged ICU care. Such individuals are known to have a high morbidity and mortality rate. No AEs specifically due to the study nutrient formulations are expected. However, we will closely monitor the clinical course of all subjects daily and record conventional serious adverse events (SAEs) and unexpected and expected AEs, as well as note significant clinical or surgical events as narrative data. For the purposes of study reporting, an SAE is any of the events below:

1. Death
2. Re-hospitalization after study PN or tube feeding discontinuation
3. Documented pulmonary aspiration of study tube feeds during study tube feed administration
4. New cancer diagnosis
5. Congenital anomaly/disorder

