When any of the above events occur, an SAE form in the subject's CRF binder is filled out and faxed to the DCC. The DCC will in turn report these events to the DSMB and NIDDK. These events will also be reported to each site's IRB per their local reporting requirements.

All other serious, unexpected or unanticipated problems that are potentially related to study PN or tube feeding will be reported to the IRB, per local reporting guidelines, and the DCC.

Operationally, this means that if: 1) in the opinion of the PI, was there a causal relationship between the intervention and the serious event (i.e., there is a reasonable possibility that the event may have been caused by the study drug intervention); and 2) the serious event was unexpected (i.e., not identified in nature, severity or frequency in the current IRB approval research protocol or informed consent document). Code responses in terms of relation to study PN will be as: definitely related, possibly related, unsure, probably not related and definitely not related). SAEs and AEs need to be reported up to and including 30 days after study drug

discontinuation. Ongoing SAEs and AEs must be followed until resolved. A 30-day post-study drug follow-up SAE/AE form will be included in subject monitoring.

Expected Adverse Events: There are no expected AEs that are likely to be due to the study PN or tube feeding. **Major AEs common in ICU subjects receiving PN and tube feeding will be identified and reported to the DCC and DSMB.** The following expected AEs would be reported during the 28-day study:

1. Clinically significant pulmonary aspiration
2. Pneumothorax
3. Development of worsening renal function with serum creatinine ≥ 5.0 mg/dL or requiring new initiation of renal replacement therapy
4. Development of severe hepatic dysfunction (serum total serum bilirubin ≥ 15.0 mg/dL)
5. Hyperglycemia > 250 mg/dL
6. Hypoglycemia < 50 mg/dL (from blood draws and laboratory analysis)

The adverse event data will be compiled by the DCC and reported to the DSMB twice a year. This trial will employ an NIH-approved data and safety monitoring board (DSMB) and a comprehensive AEs reporting plan to minimize risks to the subjects.

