The only significant difference in nutrient administration is that a different caloric dose will be given to individual patients, depending on the randomization; either 40% below the estimated REE using the standard HBE (i.e. $0.6 \times$ estimated REE), 100% of the REE (i.e. $1.0 \times$ estimated REE), or 30% above the estimated REE (i.e. $1.3 \times$ estimated REE). There is no *a priori* risk to any of these energy doses and the limited data to date are conflicting as to whether one dose confers any risk or morbidity versus another (there are no data to suggest that ICU mortality would be different at any of these three energy doses vs. the others). Further, this range of energy doses is routinely given to adult ICU patients throughout the world. This is due to the lack of consensus on appropriate energy dosing for specialized nutrition support. The total amino acid/protein and fluid amounts in each of the three energy-dose groups is designed to be similar between groups (please see research plan).

Tighter blood glucose control, generally using insulin drip therapy, is the standard of care for ICU subjects as several studies now show that control to levels in the range of < 180 mg/dL decreases ICU morbidity and mortality, although the exact goals for blood glucose remain controversial in surgical ICU patients. Recent data from the NICE-SUGAR trial suggest that maintaining blood glucose levels < 180 mg/dL may be an appropriate goal in ICU patients. However, uncertainty persists with regard to surgical ICU patients, whom may benefit from lower levels, based primarily on earlier data from the large Leuven study (some centers suggest levels lower than 140-150 mg/dL or lower in such patients). Risk of hypoglycemia is theoretically increased using this approach but with careful blood glucose monitoring (routine in ICU subjects on insulin infusion), this rarely occurs. Blood glucose control goals will be liberalized (≤ 200 mg/dL) when the subject is in the less-controlled environment of the general surgical ward.

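### Hypoglycemia counts as an adverse event only when laboratory-analysed, so bedside lows treated without a laboratory sample drop out of the safety data

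*Combined protocol and SAP*

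**What the plan says.** The relevant text in the combined protocol and SAP is in four places.

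- **Expected Adverse Events.** Two glucose items are to be reported over the 28-day study: "Hyperglycemia > 250 mg/dL" and "Hypoglycemia < 50 mg/dL (from blood draws and laboratory analysis". Only the second limits where the value may come from. Adverse event data go to the DSMB twice a year.
- **Data Collection, item D.** The study glucose values are "Three blood glucose data points (the initial AM blood glucose sent to the hospital laboratory", plus "one representative laboratory or fingerstick blood glucose level obtained at a time point between 1400-1660 h and again between 2200-2400 h". Fingerstick values are thus accepted as study data.
- **Adverse Event (AE) Reporting.** The team states that "we will closely monitor the clinical course of all subjects daily". Expected and unexpected events are recorded, and significant clinical events may be noted as narrative.
- **Potential Risks.** On insulin-based glucose control: "Risk of hypoglycemia is theoretically increased using this approach but with careful blood glucose monitoring" it is said to occur rarely. That monitoring is described as routine for patients on an insulin infusion. The number of readings a day is not given.

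**The concern.** The plan relies on close bedside monitoring to keep hypoglycemia rare, yet its definition leaves out a low found only by that monitoring. A fingerstick can enter the case report form as a glucose value and still not be a reportable event. High glucose has no such filter, so the two glucose harms are ascertained by different rules.

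This matters because glucose is a direct safety pathway for the randomised factor. The arms are created by changing PN carbohydrate and lipid. The Background names hyperglycemia as a complication of excess calories and criticises earlier energy-dose studies for not reporting blood glucose. If lows are under-counted, the DSMB sees fewer events and has less chance of noticing a difference between arms.

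**Working it through.** The plan states no detection figure, so there is none to reproduce. The main check is to follow one event through the text.

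**1. A fingerstick of 38 mg/dL at 1500 h, treated at once, with no laboratory sample (hypothetical)**
- Data Collection, item D: admissible as the afternoon study value.
- Hypoglycemia item: meets the threshold, fails the source condition, not counted.
- By contrast, a fingerstick above 250 mg/dL meets the hyperglycemia item, which names no source.

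**2. Other routes by which the low could be reported**
- The SAE list has five items: death, re-hospitalization, aspiration of study tube feeds, new cancer and congenital anomaly. Hypoglycemia is not among them.
- The route for other problems requires a serious event that is both possibly caused by the intervention and unexpected in nature, severity or frequency. Hypoglycemia is on the expected list, so an ordinary low would not qualify.
- Daily monitoring can find the low but does not change the definition. A narrative note is possible, but nothing turns it into a count in the adverse event frequency tables.

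**3. Contrast between arms**
- Total energy: 1.3 / 0.6 = 2.17-fold between the highest and lowest arms.
- With measured REE *R* and a fixed amino acid contribution *P*, the non-amino-acid ratio is (1.3*R* − *P*) / (0.6*R* − *P*). This is at least 2.17 for 0 ≤ *P* < 0.6*R*.
- Dextrose starts at 70% of non-amino-acid PN energy in every arm. Under full PN at that split, the PN dextrose ratio is therefore also at least 2.17.

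**4. Effect on the counts**

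Let λ be the true number of lows in an arm and *p* the share that also have a laboratory value below 50 mg/dL. The counted number is *p*λ. If *p* is equal across arms, the ratio between arms is kept but the difference shrinks to *p*(λ₁ − λ₂). If *p* differs by arm, the ratio is distorted too.

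**5. What *p* could be (assumptions only)**

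For an episode of *D* hours with random onset and sampling unrelated to it, the chance of being sampled is the sum over gaps of min(*D*, gap) / 24.

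- One laboratory draw a day (item D requires only the morning one): 1/24 = 4% for 1 h, 4/24 = 17% for 4 h, 8/24 = 33% for 8 h.
- Four evenly spaced laboratory draws: 4 × 1/24 = 17% for 1 h, 4 × 4/24 = 67% for 4 h.
- A laboratory sample prompted by every bedside low and taken before correction: *p* near 100%.

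The plan gives none of these inputs, so *p* could lie almost anywhere in this range.

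**6. Hyperglycemia**

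Any charted reading may count. With 12 evenly spaced readings a day the same formula gives 12 × 1/24 = 50% of 1 h episodes and 12 × 2/24 = 100% of 2 h episodes. With 24 readings it gives 100% of 1 h episodes.

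**The case against.** The strongest defence is that the laboratory condition deliberately favours specificity. Bedside meters err, and a laboratory value guards against false lows. The rule is the same in all arms under double-blinding, so no bias between arms is shown, only fewer counted events. The plan expects hypoglycemia to be rare, and a site might send a laboratory sample whenever a bedside value is low. All of this is fair. It does not remove the gap: no confirmatory sample is required, and a laboratory-confirmed row keeps the specificity without discarding the other events.

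A reader might infer more than the text supports.

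- **That most low or high glucose episodes will be missed.** Adverse event detection is not tied to the three values in item D, and any reading can count for hyperglycemia. Three values would be 3/24 = 12.5% of readings at 24 a day or 3/12 = 25% at 12 a day. Those are shares of readings, not of episodes detected.
- **That the unspecified choice of a representative value hides extremes and damages the glucose analyses.** This is speculation about recorders. Timed values suit the Aim 1 uses of glucose as a daily covariate and as means by study day and arm. The missing selection rule and the impossible clock time in "one representative laboratory or fingerstick blood glucose level obtained at a time point between 1400-1660 h" are minor clarifications.

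One objection bears on the remedy. Counts from all readings depend on how often glucose is read, and that may differ between arms if insulin need differs.

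**Conclusion.** The point holds for hypoglycemia. As written, a bedside value below 50 mg/dL without laboratory analysis is left out of the adverse event data that reach the DSMB, although the same value may stand in the study's glucose data. Under-counting is possible, but its size is unknown: the illustrative share of lows captured runs from about 4% to nearly all, depending on assumed episode length, laboratory draws per day and confirmatory practice. No loss is shown for hyperglycemia, and no bias between arms is shown. The conclusion rests on reading the parenthesis in the hypoglycemia item as a condition on the source. The morning-draw illustration also assumes that item D is collected daily, which its clock windows and the Aim 1 reference to daily glucose levels suggest. This is a cheap improvement to safety ascertainment, not a flaw in the primary analysis.

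**What to change.** In Expected Adverse Events:

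- Count hypoglycemia < 50 mg/dL and hyperglycemia > 250 mg/dL from any charted reading, laboratory or bedside.
- Record the source and time of each event.
- Report laboratory-confirmed events as a separate row by arm. For hypoglycemia this row preserves the present definition.
- Report the number of glucose readings per patient-day by arm beside the event counts, so that a difference in monitoring is not mistaken for a difference in harm.

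Keep the timed item D values for the Aim 1 glucose analyses. When the text is next edited, state how the afternoon and late-evening values are chosen and correct the end of the afternoon window.

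The cost is a case report form change and chart abstraction of events and reading counts. No extra blood is drawn, and no glucose target or treatment changes. Some bedside lows will be meter error, which comparison with the laboratory-confirmed row will help to show. Event counts will also depend on reading frequency, which is why the readings per patient-day are needed.

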
Current clinical practice guidelines, which are not evidence-based, suggest that an adequate energy goal for most adult ICU patients is approximately equivalent to measured or estimated REE x 1.0-1.3, given the minimal physical activity of ICU patients and the known complications of excess caloric doses, including hyperglycemia ^{8-10, 12}. In observational and retrospective (unblinded) studies, administration of both adequate energy doses (typically via the intravenous route well as “hypocaloric” feeding (typically as enteral feeds given at less than prescribed amounts) have each variously been associated with improved ICU outcomes in prolonged stay (> 4-5/days) ICU patients, particularly with regard to hospital-acquired infections, sepsis, and other complications ^{6, 11, 34, 35}. Villet et al showed that less negative (i.e. more positive) ICU

energy balance was associated with lower rates of hospital infections, less time on mechanical ventilation, decreased ICU length of stay (LOS) and lower total complication rates¹¹. Dvir et al found that daily mean negative ICU energy balance (energy intake – REE by indirect calorimetry) was strongly associated with increased rates of respiratory failure, sepsis, renal failure and pressure ulcers and total ICU complications⁶. In marked contrast, Krishnan et al performed an unblinded descriptive, cohort study in medical ICU patients receiving PN, EN or EN+PN and showed that death rates varied as a function of the mean daily energy intake³⁴. The patients in the lowest tertile of mean daily caloric intake in relation to a goal of 25 kcal/kg/day had the lowest mortality rates compared to the higher tertile energy intake groups. Further, Rubinson et al performed a prospective, unblinded cohort study in 138 clinically matched medical ICU patients and found that patients whom received an average of < 6 kcal/kg/day (lowest quartile of intake) had significantly more bloodstream infections (BSI) than patients in the 2nd to 4th quartile groups for energy intake³⁵. This study suggested that there might be a threshold of energy intake needed to decrease BSI in medical ICU patients, but that higher levels of caloric intake do not influence this morbidity index.

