Unfortunately, in all trials concerning ICU energy dose and outcomes, **a major design flaw is that the amino acid/protein and micronutrient intake has also varied between groups, especially when enteral feeds were employed**³⁴. Also, blood glucose levels in the study groups, a known risk factor for ICU morbidity and mortality, were either not reported^{6, 11, 35} or were higher than levels now considered appropriate for ICU patients (<150-180 mg/dL)³⁶. **Thus, the true impact of energy dose per se on clinical outcomes in ICU patients is unknown at the present time.** Studies to help better define energy dosing are also potentially important to guide clinicians to avoid complications related to overfeeding and refeeding syndromes, common in ICU settings^{12, 37-39}. **Phase III, adequately powered, double-blind, intent-to-treat RCTs are needed, with design informed by pilot data such as we will generate in this project, to better define calorie requirements associated with improved outcomes in ICU patients.**

Recent discussions have emphasized the utility of metabolomic methods for nutrition research^{40, 41}. **Metabolomics analysis represents a novel approach to study integration of metabolic responses to specialized nutrition support**^{42, 43}. We, under the direction of Co-I [name], have focused on high-resolution liquid chromatography mass spectroscopy (LC-MS) method. Metabolic profiles can be analyzed using our established bioinformatics methods to identify metabolic patterns and potential metabolic biomarkers of energy insufficiency and response to the different ICU energy dose regimens⁴⁴. **The proposed studies will allow us to generate needed data on the effect of energy dose and energy deficits on global metabolomic patterns over time that may be associated with key clinical outcomes in ICU patients.** Future studies could focus on nutritional strategies based on the specific identity of plasma metabolites that may be associated with improved outcomes. The fractal analysis-derived Hurst exponent has recently received attention because it provides a means to interpret biological signals generated by healthy biological systems or pathological states with one numerical value⁴⁵⁻⁴⁹. Hurst exponent data is related to a variety of physiologic states and to outcome measures in Parkinson's disease, obstructive sleep apnea and sudden

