Potential Risks: A total of approximately 150 mL of blood will be obtained for analysis during the first 28 days after entry. A total of 28 mL of blood will be drawn at each of the baseline and days 3, 7, 14, 21 and 28 of study. Although most of the early blood draws (e.g. baseline and days 3, 7 and 14) are likely to be via an already-indwelling arterial catheter or less likely a central or peripheral venous catheter required for clinical purposes, pain and bruising, and much less likely, infection could occur with venipuncture. Lightheadedness and fainting can also occur with drawing blood.

Indirect calorimetry to measure resting energy expenditure (MREE) is a routine ICU test and performed over a 30-minute period using a metabolic cart (to collect expired air for measurement by the machine), which is connected to the mechanical ventilator tubing in patients on mechanical ventilation. Manipulation of the tubing for this connection on a Monday-to-Friday basis (5x/week) carries an extremely small risk of infection. In patients not on the ventilator, the measurement is done while the patient is lying quietly in bed by placing a large plastic see-through hood over the head of the patient to collect the expired air. This could cause a sense of claustrophobia in some patients, but is typically very well tolerated.

Administration of PN has well-known complications that can be classified as mechanical (e.g. pneumothorax with central line insertion), infectious (e.g. PN-associated infection) and metabolic (e.g. hyperglycemia, electrolyte disturbances, increased serum liver function tests).

Administration of tube feedings can result in nausea, emesis, pulmonary aspiration, pneumonia, diarrhea, a variety of mechanical complications associated with the placement of feeding tubes and metabolic complications similar to that seen with PN. However, these modes of feeding will

be given only as indicated per standard clinical care guidelines and a central venous catheter will be inserted only if indicated per clinical care by the primary physicians.

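### The risk and adverse-event text conflicts with the protocol's own background, and no listed adverse event covers electrolyte disturbance or refeeding, so these may go uncounted by dose arm

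*Combined protocol and SAP*

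**What the plan says.** All places are in the combined protocol and SAP.

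- **Potential Risks, on dose.** The text states "There is no *a priori* risk to any of these energy doses and the limited data to date are conflicting" on whether one dose carries more risk or morbidity than another. It then adds in parentheses that "there are no data to suggest that ICU mortality would be different at any of these three energy doses vs. the others".
- **Background, on mortality and excess calories.** It describes an unblinded medical-ICU cohort in which "death rates varied as a function of the mean daily energy intake", with the lowest mortality in the lowest intake tertile. It also refers to "the known complications of excess caloric doses, including hyperglycemia".
- **Background, on the purpose of dosing studies.** One stated use is to guide clinicians "to avoid complications related to overfeeding and refeeding syndromes, common in ICU settings".
- **Adverse Event (AE) Reporting and Expected Adverse Events.** The first says that no events due specifically to the study formulations are anticipated. The second says: "There are no expected AEs that are likely to be due to the study PN or tube feeding".
- **Potential Risks, on PN in general.** Well-known metabolic complications are given as "hyperglycemia, electrolyte disturbances, increased serum liver function tests".

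**The concern.** Two pairs of statements cannot both stand as written. A mortality association is cited in the Background and denied in Potential Risks. Feeding-related events are not expected in the AE sections, but related complications are called well known or common elsewhere.

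This matters beyond wording because the AE sections fix what is counted. Energy dose is the randomized factor, and avoiding overfeeding and refeeding complications is one of the protocol's reasons for studying it. If electrolyte and refeeding events have no defined place on the form, the trial could report similar AE frequencies at 0.6, 1.0 and 1.3 x REE without having counted a class of event that its own text names. This pilot is meant to inform later Phase III trials, and safety data not collected systematically are hard to recover afterwards.

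**Working it through.** The plan states no figure on this point, so the check sets the text side by side.

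**Step 1: mortality.** Potential Risks says there are no data. The Background gives one cohort with an association. That cohort was observational and unblinded, and its intake was scaled to 25 kcal/kg/day, not to multiples of REE. It therefore does not test the three study doses. It supports saying that there are no randomized data, or that the data conflict. It does not support saying that there are none. The concession earlier in the same sentence concerns risk or morbidity, and the parenthesis then excludes mortality from it.

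**Step 2: named harms against the six items under Expected Adverse Events.**

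| Harm named in the protocol | Where named | On the six-item list? |
|---|---|---|
| Hyperglycemia | Background; Potential Risks | Yes, above 250 mg/dL |
| Raised liver tests | Potential Risks | Only as severe dysfunction, bilirubin at or above 15.0 mg/dL |
| Electrolyte disturbances | Potential Risks | No |
| Refeeding syndrome | Background | No |

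The other four items are aspiration, pneumothorax, worsening renal function and hypoglycemia below 50 mg/dL. Electrolyte or refeeding items: 0 of 6.

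**Step 3: other reporting routes.**

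- The SAE list has five items: death, re-hospitalization, aspiration of tube feeds, new cancer and congenital anomaly. Electrolyte or refeeding items: 0 of 5.
- The catch-all opens broadly, but its operational definition requires a serious event that the investigator judges causally related and that is unexpected. Unexpected means not already identified in nature, severity or frequency in the approved protocol or consent document. Potential Risks already identifies electrolyte disturbances in nature. A serious one can therefore be classed as not unexpected, although unusual severity might still qualify it. A non-serious one does not qualify.
- AE Reporting also promises general recording of expected and unexpected AEs, with significant events noted as narrative. It names no electrolyte or refeeding event.

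**Step 4: tabulation.** Statistical Analysis says that adverse events will be described in frequency tables. It does not say that these will be by dose arm.

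**Step 5: what counting could show (context only).** The rates below are assumptions. With n = 20 per arm, the chance of at least one event is 1 - (1 - p)^20:

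- p = 2%: 1 - 0.98^20 = 0.33
- p = 5%: 1 - 0.95^20 = 0.64
- p = 10%: 1 - 0.90^20 = 0.88

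If an arm has 0 of 20, the one-sided 95% upper bound is 1 - 0.05^(1/20) = 0.139. Even complete counts would be descriptive, and an empty cell would still be compatible with a rate of nearly 14%.

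**The case against.** The best defence is that the plan already covers most of what matters. Hyperglycemia, the only excess-calorie complication the Background names, is on the list, and glucose is recorded three times a day and modelled by dose group. Infection is the primary endpoint. Death is an SAE, and 28-day mortality is compared between arms. The DSMB receives AE data twice a year and gets unblinded as well as blinded reports. Expected Adverse Events also promises that major events common in ICU patients on PN and tube feeding will go to the DCC and DSMB. On mortality, the sentence is confined to the three study doses, and the Background itself warns that protein and micronutrient intake varied between groups in earlier studies.

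Most of this stands, and it rules out several stronger inferences:

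- That the AE list misses overfeeding harm altogether. It does not.
- That the list was derived from the mortality statement. Nothing in the documents says so.
- That the DSMB cannot see results by arm. It can, for whatever is collected.
- That the risk section hides PN complications. It lists them; the statements that none are expected are in the AE sections.
- That patients' representatives were misinformed. The consent pages are not available, so this cannot be checked.
- That the cohort shows one study dose to be safer. Its design and scale do not allow that.
- That the calorie contrast between arms measures the harm missed. It says nothing about event counts.

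The defence does not answer the electrolyte and refeeding gap. The promise about major common events leads straight into the six-item list, and narrative notes are not a count by arm.

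**Conclusion.** The concern holds in a limited form. The absolute statement on mortality, the claim of no prior risk and the statements that no feeding-related events are expected are inconsistent with the Background and with the PN complications listed in Potential Risks. Separately, electrolyte and refeeding events appear in none of the six expected-AE items and none of the five SAE items, and the catch-all may exclude electrolyte disturbances because the protocol already names them. They may therefore not be counted by dose arm.

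The size in events is unknown because the documents give no rates. The conclusion rests on reading the operational definition of the catch-all as the rule that sites would apply. If sites recorded every AE under the general promise, the gap would shrink to one of definition and tabulation. The point merits an amendment. It does not undermine the primary infection analysis or the mortality comparison.

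**What to change.** 1. **Reconcile the text.** Bring AE Reporting, Expected Adverse Events and the dose paragraph of Potential Risks into line with the Background and with the PN complications in Potential Risks. For example, state that there are no randomized data, that observational data conflict and include a mortality association, and that excess calories have known complications. Make matching changes wherever the same risk text is reused.
2. **Close the counting gap.** Add electrolyte disturbance and refeeding events to the 28-day AE form, taken from clinically ordered tests. The investigators should set the definitions, since the documents name no analytes or cut-offs for these events.
3. **Tabulate by arm.** Show these events with the other listed AEs by dose group in the unblinded DSMB reports and the final AE tables.

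The cost is an amendment to the risk text and AE form and more AE entries, with no new tests. Ascertainment will depend on how often clinicians order the relevant tests, so the tables should say so. No change to dosing or treatment is proposed.
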